### VII.E.1 Will subjects be randomized? Yes

VII.E.1.a Will any subjects be blinded to which study arm they have been assigned?

Yes

VII.E.1.b Does the protocol permit telling subjects their treatment assignment at the end of the entire study?

Yes

VII.E.1.c Describe the circumstances under which subjects will be told what study arm they have been assigned.

At the end of the study, or after an adverse event that the subject is withdrawn from the study.

VII.E.2 Describe randomization scheme/assignment including ratio such as 1:1, 2:1 etc.

Subjects will be randomized 2:1 to salsalate or placebo, respectively so their is 2/3 chance they will be randomized to salsalate and 1/3 to placebo. This scheme was chosen to ensure proper effect sizes can be determined in the salsalate group in this pilot study. The obese non-prediabetc group will not be randomized and only undergo baseline testing.

VII.E.3 Will any questionnaires, surveys, or written assessments be used to obtain data directly from subjects in this study?

Yes

VII.E.4 List all questionnaires, surveys, written assessments and ATTACH each one to the application. (NOTE: You are NOT prohibited from attaching copyrighted materials to this application)

Phone screening questionnaire
Demographics and Contact Info questionnaire
Health History questionnaire
Modifiable Activity Questionnaire (MAQ)

3 Day dietary record (CRU bionutrition)

Salsalate screening log

VII.E.5 Does this project involve creating any audiotapes, videotapes, or photographs?

No

VII.E.6 Provide a detailed description in sequential order of the study procedures following the consent process - DO NOT cut and paste from the Consent Document.

Describe study populations separately if they will be participating in different procedures - include CONTROL population if applicable.

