#### **DESCRIBE:**

- What subjects will be asked to do/what happens in the study (in sequential order)
- The time period over which procedures will occur
- The time commitment for the subject for individual visits/procedures
- Long-term followup and how it occurs

Experimental design. A total of 30 obese (defined as body mass index >30 kg/m2) adults age 18-49 years with prediabetes will be enrolled and randomized to 4-5 weeks of Salsalate or placebo in a randomized (2:1), double-blind, placebo controlled, parallel study design. Subjects will orally ingest 3000 mg/day (1500 mg in a.m. and 1500mg in the p.m.) of Salsalate (n=20) or placebo (n=10) for 28-35 days. A total of n=10 obese NON-prediabetic CONTROL subjects will be enrolled to establish prediabetes-related differences in obese adults primary outcomes at baseline. Therefore, a total of 40 subjects will be enrolled. The non-prediabetic control subjects will undergo screening (Visits 1 and 2) and baseline experimental testing (Visits 3, 4) but will NOT undergo the Salsalate/placebo intervention or visits 5, 6 or 7. Prediabetes will be defined as fasting (at leaset 8 hour fast) blood glucose between 100-126 mg/dl, a fasting blood glucose of 140-199 mg/dl at 120 min during an oral glucose tolerance test, or HbA1C between 6.0 – 6.5%.

Order of visits. Subjects will undergo experimental testing at baseline and again after the 4-5 weeks of Salsalate or placebo. Subjects will be studied between 7:00 and 10:00 am in the Clinical Research Unit (CRU) in the Institute for Clinical and Translational Science (ICTS) at the University of Iowa following an 8 hour overnight fast. The order of visits are as follows and will occur over a period of 7-8 weeks (see TABLE 1 attachment for summary of visits):

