#### Visit 1 (3.5 hours): Consent and Screening

- a. Explanation of the study; reading and signing of written informed consent b. If subject consents but requires a 2-week washout for aspirin, salicylate, NSAID, vitamin, supplements, they will be scheduled to complete the Visit 1 in 2 weeks. If subject consents and no washout is needed, screening tests will be performed same day to determine eligibility by the following:
- i. Research staff will obtain resting vitals (blood pressure, heart rate)
- ii. Research staff will obtain anthropometrics including weight, height, waist and hip circumference with tape measure.
- iii. Research staff will obtain resting 12-lead ECG
- iv. Subject will fill out the Demographics and Health History survey, and the Modified Activity Questionnaire (MAQ)
- v. Research nurse or trained staff will obtain venous blood draw using butterfly needle for UIHC pathology labs:
- Creatinine, Lipid panel, TSH(4.5 ml blood- 1 light green PST tube)
- Complete blood count(4.5 ml blood- 1 lavender tube)
- Subject will undergo oral glucose tolerance test (OGTT): Subject will consume a beverage containing 75 grams of glucose. Blood samples will be collected at timed intervals of baseline, 1 hour and 2 hours after consuming beverage for glucose and insulin. Total blood collected for insulin and glucose for OGTT: 13.5 ml blood (4.5ml x 3 PST tubes).
- TOTAL blood collected for Visit 1: 22.5 ml (1.5 Tablespoons)

- Visit 2 (2 hours): Dietary food record, cerebral blood flow velocity
- a. Meet with CRU bionutritionist for instruction on 3-day dietary record to return on visit 3
- b. Middle cerebral artery blood flow velocity using transcranial dopper during the following protocol to measure cerebral vasoreactivity to hypercapnia:
- -After 3 min of normal breathing, subjects will perform 2, 30 second breathholds sparated by 3 min.
- -Next, After 3 min of room air breathing, 3 min of breathin 2%CO2, 3 min of breathing 4%CO2 (balanced with 21%O2 and N) will be performed followed by 3 min of room air breathing.
- c. Subject will be instrumented with 24 hour blood pressure monitor to wear home for 24 hours. Subject will return it to the investigators when come in for Visit 3. There is no long term follow up.
- Visit 3 (3 hours): 1st Baseline experimental visit (Blood, Endothelial cells, FMD, PWV and Retina scan)
- a. Subject arrives at the CRU between 7-10 am after overnight 8 hour fast

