- b. Subjects on vasoactive medications will be asked to hold medication on the morning of experimental visits but to bring the medications with them to be taken after the visit.
- c. Return 3-day dietary recall
- d. IV catheter, endothelial cell collection and blood sample: Subject will lie supine and research nurse will insert venous 18 G catheter into antecubital vein.
- e. Research staff or physician will perform J wire endothelial cell collection (3 wires) via 18 G catheter.
- f. After 20 min, nurse practitioner will then obtain blood samples thru catheter:
- Lipid panel, insulin, hs-CRP, salicylate, creatinine, AST/ALT (4.5 ml blood- light green PST tube)
- Catecholamines (8 ml blood- 2 x 4 ml Na+ Hep green top tubes)
- HbA1c (4.5 ml blood- 1 x 4.5 ml lavender top tubes)
- Extra blood collected for specialized labs performed in PIs lab:

Serum: 17 ml blood-  $2 \times 8.5$  red/gray top SST tube) for interleukin-6, tumor necrosis factor-alpha.

Whole blood (17 ml blood-  $3 \times 8.5$  ml Citrate PPT tube) for mononuclear cell DNA isolation.

- f. After 15 min supine rest the following non-invasive vascular measurments are obtained by the PI and his research staff:
- 1) Radial, brachial, carotid and femoral waveforms non-invasively for PWV assessment
- 2) Carotid artery compliance using ultrasonography
- 4) Brachial artery flow-mediated dilation (FMD) with ultrasound
- 5) Brachial artery dilation after 0.3 mg sublingual nitroglycerin with ultrasound
- g. Subject escorted to the CRU Human Cardiovascular Research Lab and a physician or research staff trained in microneurography will insert needle into peroneal nerve for measurement of muscle sympathetic nerve activity
- h. Subject will meet with bionutritionist and review 3-day food record with subject
- i. Subject receives meal/snack from CRU bionutrition and then can leave
- \*\*TOTAL blood collected for Visit 3= 68 ml (~4.5 tablespoons)

Visit 4 (4.5 hours): 2nd Baseline experimental visit (Forearm Blood Flow and Microneurography)

- a. Subject comes to the CRU Human Cardiovascular Research Lab in the CRU between 7-10am after 8 hour overnight fast
- b. Subject will be instrumented with upper arm venous occlusion cuffs and wrist cuffs

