for measurements of forearm blood flow using venous occlusion plethysmography c. A physician trained in brachial artery catheterization in the Human Cardiovascular Research Lab will then perform brachial artery catheterization with 27 G needle and undergo incremental infusions of saline, acetylcholine, acetylcholine + vitamin C (ascorbic acid), and sodium nitroprusside + vitamin C (see Expermental Procedures for details)

- d. Subject will be escorted to Dept of Ophthalmology in Pomerantz Bldg and have picture of retinal performed (scan takes  $\sim$ 10 min)
- e. Subject will be given snack or lunch in CRU.
- f. Subjects will be randomized in a 2:1 scheme to Salsalate or placebo
- g. Nurse will dispense 35 day supply (210 tablets) of Salsalate (dose 3000 mg/day = 500 mg tablets x  $6/\text{day} \times 35 \text{ days} = 210 \text{ tablets}$ ) or placebo
- h. Subject will take first dose of Salsalate (500 mg x 3 pills) or placebo at CRU and 2nd dose (1500 mg) at home in evening- this is Day 0

Visit 5 (45 min) ~Day 14: Subject will return to CRU for venous blood sample to measure serum salicylate (4.5 ml x 2 PST tubes: total 9 ml or ~0.5 tablespoons), Blood pressure, HR and survey of any side effects. If any side-effects/symptoms present, nurse coordinator will follow instructions as outlined in section VIII.2 "Plan for Managing Risks". Subject will receive 3-day food record booklet from CRU bionutritionist

Days 25: Coordinator or research staff will call subject in the evening to remind subject to start 3-day dietary record on days 26, 27, 28.

Visit 6 (5 hours) Betwee Day 26-34: Post-experimental visit #1 (FMD, PWV and Retina)

- a. Subject will take morning dose of Salsalate/placebo and return to CRU between Day 26 -35 for venous blood sample to measure serum salicylate, blood pressure, HR; and survey of any side effects
- b. All vascular measurements of Visit 3 will be repeated
- c. Middle cerebral artery blood flow velocity using transcranial dopper during the following protocol to measure cerebral vasoreactivity to hypercapnia:
- -After 3 min of normal breathing, subjects will perform 2, 30 second breathholds sparated by 3 min.
- -Next, After 3 min of room air breathing, 3 min of breathin 2%CO2, 3 min of breathing 4%CO2 (balanced with 21%O2 and N) will be performed followed by 3 min of room air

breathing.

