- d. Subject escorted to the CRU Human Cardiovascular Research Lab and a physician or research staff trained in microneurography will insert needle into peroneal nerve for measurement of muscle sympathetic nerve activity
- e. Subject will be instrumented with 24 hour blood pressure monitor to wear home for 24 hours. Subject will return it to the investigators when come in for Visit 7. There is no long term follow up.

Total blood collected for visit 6: 68 (~4.5 Tablespoons)

Visit 7 (3 hours) Between Day 27-35: Post-experimental visit #2

- a. Subject will take morning dose of Salsalate/placebo return to CRU on Day 27 or 28 for venous blood sample to measure serum salicylate, AST/ALT and creatinine (0.5 ml blood)
- b. All measurements from Visit 4 will be repeated
- c. Blood draw for salicylate, insulin, lipid panel, creatinine, ALT/AST (1  $\times$  4.5 ml lt green PST tube)
- d. Total blood collected for visit 7: 4.5 ml ( $\sim$ 1/3 tablespoon)

GRAND TOTAL Blood drawn over course of study: 172 ml (~11.5 tablespoons)

Screening Methods.

- a) Blood pressure, ECG. Subject will undergo resting BP in a private CRU exam room after 15 minutes of rest. BP will be measured in supine position in triplicate separated by 2 min with an automated oscillometric BP machine under quiet, comfortable laboratory conditions. All BPs throughout study will be performed in this identical manner. A resting supine 12-lead ECG will be recorded by placing 10 electrodes on chest and recording the ECG.
- b) History and Physical exam. Prior to the experimental visit (Visit 3), subjects will undergo a complete medical history and physical examination by [name] or a CRU nurse practitioner.
- c) Blood chemistries: After passing the physical exam standard blood chemistry analysis will be obtained under fasting conditions including a basic metabolic panel, lipid panel, HbA1C, complete blood count, TSH and FSH (for women only).

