determine that a neurogram represents sympathetic activity to muscle or skin: We have used this technique safely in over 2000 studies since February 1984 and it is well tolerated and reproducible. The mental stress test is a non-baroreflex mediated sympathoexcitatory stimulus used to test sympathetic responsiveness. This test requires that each subject to subtract continuously the number 7 from a 3-digit number as quickly and as accurately as possible for 3 minutes. During the test, the participants are intentionally frustrated by being asked to calculate faster and by being corrected in case of wrong answers. This stimulus has little effect on muscle SNA and increases forearm blood flow.

c) 24-hour ambulatory blood pressure variability and baroreflex sensitivity. Twenty-four hour systolic blood pressure will be recorded using standard ambulatory blood pressure assessment (90207-IQ, Spacelabs Healthcare, Inc)and 24 hour blood pressure variability determined from the standard deviation of systolic and mean blood pressure recordings. Baroreflex sensitivity will be determined by recording blood pressure and heart rate continuously for 15 minutes during visit 3 and 6 using via beat-to-to beat finger blood pressure (Finometer MIDI, Finopress Medical Systems) and calculated using the sequence technique.

Microneurography training controls:

We will recruit 20 additional healthy control volunteers who will have microneurography performed on them by [name]. The training will be provided by [name] and [name], both of whom are highly trained in the technique and will provide close oversight in the training. The 20 volunteers will sign and separate consent form (see attached) and will be compensated \$25.

- VII.E.7 Will you attempt to recontact subjects who are lost to follow-up?

  No followup is not required in this study
- VII.E.9 Will subjects be provided any compensation for participating in this study?

  Yes
  - VII.E.10 Cash

No

VII.E.11 Gift Card

No

VII.E.12 Check

Yes

VII.E.13 Who will be providing the research compensation check to the subject?

Accounting Services directly via the e-Voucher system

VII.E.16 Other

No

- VII.E.19 Describe the compensation plan including
  - · Compensation amount and type per visit
  - Total compensation
  - Pro-rating for early withdrawal from study

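### The visit windows allow Visit 7 on the morning after Visit 6, and then the follow-up ambulatory blood pressure recording can last only 16-22 hours instead of the stated 24.

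*Combined protocol and SAP*

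**What the plan says.** All of this is in section VII.E.6 unless noted.

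- **Follow-up recording.** Visit 6 step e reads: "Subject will be instrumented with 24 hour blood pressure monitor to wear home for 24 hours". On hand-in it says: "Subject will return it to the investigators when come in for Visit 7". No later step is listed for that visit.
- **Clock times.** The paragraph on the order of visits has subjects studied between 07:00 and 10:00 after an overnight fast.
- **Day windows.** The Visit 6 heading is "Visit 6 (5 hours) Betwee Day 26-34: Post-experimental visit #1". The Visit 7 heading gives Days 27-35, but its step a has the subject "return to CRU on Day 27 or 28 for venous blood sample". No minimum interval between the two visits is stated, and no minimum length for a usable recording.
- **Visit 7 procedures.** All Visit 4 measurements are repeated. These include venous occlusion cuffs on the upper arms and brachial artery catheterisation.
- **Baseline recording.** The monitor is fitted at the 2-hour Visit 2 and handed in at Visit 3. A 3-day food record is taught at Visit 2 and returned at Visit 3.
- **Use of the data.** Systolic pressure is recorded over 24 hours, with "24 hour blood pressure variability determined from the standard deviation of systolic and mean blood pressure recordings".
- **Analysis (section XI.1).** The critical test is the treatment-by-time interaction. Pre-post contrasts within each arm and correlations of changes after salsalate are also planned.

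**The concern.** The instruction to record for 24 hours and the instruction to hand the monitor in at Visit 7 cannot both be met when Visit 7 is the next morning, and the plan permits that spacing. The hours lost lie between 07:00 and 15:00, so a short recording gives more weight to sleep. Both its mean and its SD then move for reasons unrelated to treatment. Baseline recordings are not cut in this way, so the change from Visit 2 to Visit 6 would mix any drug effect with a change in recording length. A within-arm contrast has no placebo subtraction to remove that shift. Section XI.1 expects only small changes after salsalate and lists systolic pressure as a possible one, so a spurious fall would run in the hoped-for direction. Hours that were never recorded cannot be recovered in the analysis.

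**Working it through.** **Inputs.** Arrival is between 07:00 and 10:00; a 5-hour visit cannot fit inside a 3-hour window, so I read the window as arrival time. Visit 6 lasts 5 hours. Fitting comes last, because the form asks for this: "Provide a detailed description in sequential order of the study procedures following the consent process". The recording must stop at Visit 7, when the upper arms are needed for the occlusion cuffs.

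**Available time.** Hours = 24 × (days from Visit 6 to Visit 7) + Visit 7 arrival − (Visit 6 arrival + 5).

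| Gap | Shortest (Visit 6 at 10:00, Visit 7 at 07:00) | Longest (Visit 6 at 07:00, Visit 7 at 10:00) | Same arrival time |
|---|---|---|---|
| 1 day | 24 + 7 − 15 = 16 h | 24 + 10 − 12 = 22 h | 24 − 5 = 19 h |
| 2 days | 48 + 7 − 15 = 40 h | 48 + 10 − 12 = 46 h | 48 − 5 = 43 h |

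The plan's 24 hours is out of reach with a 1-day gap and comfortably available with 2 days. On a next-day schedule, reaching 24 hours would need fitting by 10:00, that is, Visit 6 finished in 3 hours. The loss is 24 − 22 = 2 h to 24 − 16 = 8 h, or 8% to 33% of the day.

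**Baseline.** With a 2-hour visit, the same arrival window and a 3-day gap, the range is 72 + 7 − 12 = 67 h to 72 + 10 − 9 = 73 h. A full 24 hours fits.

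**Which day pairs are permitted.** Under the headings (Visit 6 on Days 26-34, Visit 7 on Days 27-35) there are 9 + 8 + … + 1 = 45 ordered pairs, of which 9 are next-day. Under step a of Visit 7 there are three pairs, (26, 27), (26, 28) and (27, 28), of which two are next-day. These are counts of what is allowed, not frequencies.

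**Size of the artefact (illustration).** The following are my assumptions and are not in the documents: sleep from 23:00 to 07:00, a day-night systolic difference D of 10-20 mmHg, and an SD of 10 mmHg within day and within night. Let n be the share of the recording that is night.

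- n = 8/24 = 0.333 for a full recording, 8/22 = 0.364 at 22 h, and 8/16 = 0.500 at 16 h.
- Shift in mean = −(n − 1/3) × D. Smallest: −(0.364 − 0.333) × 10 ≈ −0.3 mmHg. Largest: −(0.500 − 0.333) × 20 ≈ −3.3 mmHg.
- SD = √(100 + n(1 − n)D²). At D = 10 it goes from 11.06 (24 h) to 11.10 (22 h), a rise of 0.04. At D = 20 it goes from 13.74 (24 h) to 14.14 (16 h), a rise of 0.40.

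These shifts apply to a subject with next-day visits. The average shift in an arm is this figure times the fraction of its subjects seen on consecutive days. The documents do not give that fraction, so the arm average lies between 0 and the full shift.

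**The case against.** The strongest reply is that Visit 7 is where the monitor is handed in, not where the recording is defined to end. The text asks for 24 hours of wear, and any gap of two or more days delivers it. That stands: the defect is conditional on next-day visits. A reader might infer that every follow-up recording is short, or that the two recordings are never comparable in length. The documents do not support either.

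A reader might also infer from Day 27 or 28 that next-day visits are the usual case. That line conflicts with its own heading. It also fits poorly with the food record, which is kept on Days 26-28 and is meant to cover the three days before Visit 6. Yet even if Visit 6 cannot come before Day 29, the pair (29, 30) remains permitted, so the gap in the plan stays. The text refers to an attached Table 1 of visits that is not among the documents; it might settle the interval.

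A third objection is that the confirmatory comparison is safe. That also stands. Both arms follow the same schedule under double-blinding, so the interaction is not biased in expectation. Chance imbalance in spacing between 20 and 10 subjects is noise. Carotid-femoral pulse wave velocity is the primary outcome (section XI.2), neither aim names ambulatory pressure, and baroreflex sensitivity comes from a separate 15-minute recording. The variability outcome is an SD, for which the illustrated shift is the smaller one.

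Finally, a reader might argue that conditions differ whatever the gap, because the follow-up recording starts after nitroglycerin and after held medication: "Subjects on vasoactive medications will be asked to hold medication on the morning of experimental visits". This is weak. Section V.8 gives nitroglycerin a 30-minute duration of action, and cerebral Doppler and microneurography are listed before the monitor. Section VI.13 applies the hold on the morning of testing, and Visit 2 includes cerebral reactivity testing, so an absence of any hold at baseline is not established.

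**Conclusion.** The point holds in conditional form. The plan permits Visit 7 on the morning after Visit 6. In that case the stated 24-hour recording shrinks to 16-22 hours, with mostly or entirely waking hours missing, while the baseline schedule leaves room for the full 24. For those subjects the within-arm pre-post contrast in ambulatory pressure and its SD is distorted. The treatment-by-time interaction gains noise only.

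The 16-22 hours rests on three readings: 07:00-10:00 is arrival time, Visit 6 takes its stated 5 hours, and the monitor is fitted last. The mmHg figures rest on the outside assumptions given above and show order of size only. How many subjects would be affected cannot be determined from the documents. The consequence is modest because this is not the outcome that sized the trial, but it is worth correcting because the change is small.

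**What to change.** 1. Require at least two calendar days between Visits 6 and 7. Under the headings this leaves 45 − 9 = 36 permitted day pairs, with Visit 6 on Days 26-33 and Visit 7 on Days 28-35.
2. Reconcile the Visit 7 heading with its step a. As step a is worded, only the pair (26, 28) would satisfy the two-day rule.
3. State in section XI.1 that if a follow-up recording is still short, baseline and follow-up are compared over the same clock hours. This needs the start and stop times of each recording to be kept.

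The cost is a wording change and slightly tighter scheduling. For women, both visits must also fit the 8-day menstrual-phase window in section VI.13. No procedure is added. Moving the baseline fitting from Visit 2 to Visit 3 is not needed: the current baseline schedule already allows 24 hours, and the move would add a spacing constraint between Visits 3 and 4.
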